We anticipate that the R2R-TBI intervention will be effective in both ameliorating problems evident at baseline and in preventing emergence of additional problems in family and child functioning at one and six-months post-baseline. To test this hypothesis, we will examine group differences in family functioning (FAD-GF, Epstein, Baldwin, & Bishop, 1983), family burden of injury (FBI, Burgess et al., 1999) and child socioemotional functioning (PedSQL Psychosocial Summary Score, Varni et al., 1999) at one and six-months post-baseline.

Hypothesis 3: We hypothesize that treatment effects will be moderated by household income and level of caregiver distress at baseline.

We expect families with greater social disadvantage (lower income, more stress) will benefit most from the R2R-TBI intervention. This hypothesis is consistent with previous research findings (e.g., Antonini et al., 2014; Raj et al., 2014b; Wade et al., 2012, 2015).

Variable distributions will be examined before carrying out inferential statistical procedures, and transformations will be made in cases where distributions are skewed or fail to meet the assumptions of normality. Non-parametric procedures will be employed in cases where transformations would be inappropriate or where analysis of frequencies is justified. Preliminary work will also involve computation of reliabilities and creation of derived variables that summarize performance on measures that are highly inter-correlated. To evaluate potential attrition bias, caregivers who drop out (i.e., those who access < 3 modules and/or who do not complete baseline or follow-up measures) will be compared to those who remain in follow-up on background characteristics as well as on outcomes measured prior to dropout. Factors related to dropout will be included as covariates in the analysis.

Analytic plan for hypotheses 1 and 2. The primary analysis will consist of a linear mixed-effect models used to examine changes in caregiver, family, and child functioning among participants in the R2R-TBI intervention and IRC groups from baseline to 6-months post-baseline. In addition, the one-month data will be included in a mixed model repeated measures analysis. This model allows for flexible modeling of the pattern of change in outcomes over time and uses all the data for a given participant, even if that participant is not seen at all assessments, allowing us to retain participants with missing assessments.

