Analytic plan for hypothesis 3. Existing literature and findings from our other studies suggest that demographic factors such as household income as well as baseline caregiver functioning impact adaptation to injury, and we hypothesize that these factors will moderate the efficacy of the intervention. Hierarchical multiple regression analyses which include the interaction of group, moderator (household income, baseline functioning), and time in the model will be used to test hypothesis 3. Variable selection using backward elimination will be used to remove non-significant higher- and then lower-order terms. In order to avoid selection bias, bootstrapping will be used on the backward elimination process (Austin, 2008). Post hoc analyses will be used to compare

treatment groups on each outcome at different levels of the moderators at 1 and 6-months post-baseline.

6. Data Management

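### The hypothesis 3 plan lets backward elimination remove the pre-stated moderation terms, so a non-significant interaction has no estimate or confidence interval in the final model

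*Combined protocol and SAP*

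**What the plan says.** All the relevant text is in section 5.1 of the combined protocol and SAP.

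- **Hypothesis.** It states that "treatment effects will be moderated by household income and level of caregiver distress at baseline", and expects more disadvantaged families to gain most. Moderators and direction are therefore fixed in advance.
- **Model for hypotheses 1 and 2.** "Analytic plan for hypotheses 1 and 2. The primary analysis will consist of a linear mixed-effect models", with the one-month data brought in through a repeated-measures mixed model that retains caregivers with missing visits.
- **Model for hypothesis 3.** A separate paragraph names "Hierarchical multiple regression analyses which include the interaction of group, moderator (household income, baseline functioning), and time in the model". It does not mention within-caregiver correlation or missing visits.
- **Selection.** "Variable selection using backward elimination will be used to remove non-significant higher- and then lower-order terms". No significance level is given and no term is protected.
- **Safeguard.** "In order to avoid selection bias, bootstrapping will be used on the backward elimination process", with a citation but no rule for retaining terms or for forming estimates.
- **Follow-on analyses.** Post hoc analyses will compare "treatment groups on each outcome at different levels of the moderators at 1 and 6-months post-baseline".

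Nothing commits the sponsor to report every pre-stated interaction with its interval.

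**The concern.** Backward elimination is a tool for choosing among candidate covariates. Here the candidates include the interactions that constitute the hypothesis.

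If such a term is dropped, the final model gives no estimate and no interval for it. A true absence of moderation and a trial too small to show moderation then look the same. The post hoc contrasts do not fill the gap: from a model without the group by moderator terms, the treatment contrast at a given visit is the same at every moderator level. If the term is kept, it is reported because it passed a significance filter.

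At stake is one of three stated hypotheses: whether low-income or more distressed caregivers benefit most.

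A second, conditional concern is that the mixed model is stated for hypotheses 1 and 2 only. If *hierarchical* means blockwise ordinary regression on stacked visits, the standard errors ignore the correlation between a caregiver's visits.

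**Working it through.** The plan gives no power, effect size, SD or selection threshold for hypothesis 3, so there is no figure to reproduce. The size below rests on stated assumptions.

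**Inputs from the documents.** At most 200 participants (section 3.5); equal allocation (section 3.5); follow-ups at about 1 and 6 months (sections 4.1.5 and 5.1).

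**Assumed.** N = 200 with complete data; outcome and moderator in SD units; correlation rho = 0.5, 0.6 or 0.7 between any two visits; baseline adjustment; two-sided 5% level; true moderation b of 0.1 to 0.4 SD per SD, equal at both visits; contrast averaged over the two visits.

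**1. Standard error.**
- Variance of group by moderator at one visit = 4(1 − rho²)/N.
- Residual correlation between visits r = rho/(1 + rho).
- Variance of the averaged contrast = one-visit variance × (1 + r)/2.
- rho = 0.5: 4 × 0.75/200 = 0.0150; r = 0.333; 0.0150 × 1.333/2 = 0.0100; SE = 0.100.
- rho = 0.6: 4 × 0.64/200 = 0.0128; r = 0.375; variance 0.0088; SE = 0.094.
- rho = 0.7: 4 × 0.51/200 = 0.0102; r = 0.412; variance 0.0072; SE = 0.085.

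**2. Chance of non-significance and mean estimate given significance.** With d = b/SE:
- P(non-significant) = Phi(1.96 − d) − Phi(−1.96 − d).
- Mean given significance = b + SE × [phi(1.96 − d) − phi(1.96 + d)]/P(significant).

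Example, b = 0.2 and rho = 0.5: d = 2.0 and P(non-significant) = 48.4%. The mean given significance is 0.277, or 1.39 times the truth; the mean given non-significance is 0.118. Combined, 0.516 × 0.277 + 0.484 × 0.118 = 0.200. The full set of estimates is unbiased; the significant ones alone are not.

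| True b (SD per SD) | Non-significant, rho 0.5 to 0.7 | Mean estimate if significant ÷ truth |
|---|---|---|
| 0.1 | 83% to 78% | 2.5 to 2.1 |
| 0.2 | 48% to 35% | 1.39 to 1.24 |
| 0.3 | 15% to 6% | 1.09 to 1.03 |
| 0.4 | 2% to 0.3% | at most 1.01 |

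For b = 0.2, the estimates lost when the term is dropped average 0.11-0.12, and their 95% intervals cover 0.2 in 93-95% of those trials. That is usable information.

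**3. What elimination itself changes.** Simulation for b = 0.2, rho = 0.5/0.6/0.7:
- Full model without elimination: significant estimates average 1.38/1.32/1.24 times the truth.
- Elimination that keeps a two-way term under a retained three-way term: kept estimates average 1.35/1.30/1.22 times the truth, and the term is dropped in 46/41/33% of trials.

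Inflation among significant results is therefore much the same either way. The difference is that the non-significant estimates disappear.

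**4. The bootstrap.** A simpler simulation used one measurement per caregiver, N = 200, residual SD 1, true b = 0.20 and 150 resamples.
- No bootstrap: mean kept estimate 0.368.
- Kept if selected in at least 50% of resamples: 0.365. At least 60%: 0.392. Neither reduces the overstatement.
- Averaging the bootstrap coefficients, with zero when not selected: 0.31 when kept, but 0.14 over all trials. The overstatement shrinks only partly, and the average over all trials is too low.

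**5. Conditional point.** For ordinary regression on two stacked, baseline-adjusted follow-up visits, at rho = 0.5/0.6/0.7:
- Group by moderator type I error = 2[1 − Phi(1.96/√(1 + r))] = 9.0/9.5/9.9%.
- Three-way term = 2[1 − Phi(1.96/√(1 − r))] = 1.6/1.3/1.1%.

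Under a multilevel model this error does not arise.

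**The case against.** The strongest reply is that elimination does little harm of its own. This largely stands. Non-significance is one minus power with or without it, and step 3 shows the same inflation among significant results in the full model. A reader might infer that the procedure costs power, raises false positives or causes the inflation; the figures do not support that. Selective reporting remains.

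Other replies:

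- **The full model is fitted first, so its estimates could be reported.** True, and the plan does not say that they will be withheld. The defect is that the final model lacks them and nothing commits to reporting them.
- **Selection bias is already addressed by the bootstrap.** It is a genuine stated safeguard, and the cited source, not available here, may give a rule. The plan gives none, and a bootstrap of the selection step does not by itself supply an interval for a dropped term.
- ***Hierarchical* may mean multilevel.** It may. A reader might infer that hypothesis 3 is certain to ignore within-caregiver correlation; the text shows only that the handling is unstated.
- **The post hoc contrasts answer the question.** Not from a model without the interaction. A reader might picture separate tests in subgroup halves, but the plan does not state that analysis, so no error rate is attached to it.
- **The second moderator changes from place to place.** Mostly answered. Family functioning appears in section 5.1 as an example, and the text then specifies low income and high caregiver distress. The later "demographic factors such as household income as well as baseline caregiver functioning impact adaptation to injury" is looser, but the real gap is that no distress measure is named.

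**Conclusion.** The point holds as one of selective reporting and incomplete specification. Pre-stated moderation terms can be removed by significance, and a removed term has no estimate or interval in the final model. How often depends heavily on the true moderation, for which the documents give no value: from about four trials in five at 0.1 SD per SD to 2% or fewer at 0.4, at the maximum sample size with complete data. Fewer caregivers would raise these proportions; at N = 160 the 0.2 case becomes 44-57%.

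The type I error figures apply only if ordinary regression on stacked visits is meant. The analysis of hypothesis 1 is not affected. The change is worth making because it is cheap and makes hypothesis 3 interpretable whatever the result; it does not bear on the validity of the trial's main comparison.

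**What to change.** Rewrite the analytic plan for hypothesis 3 in section 5.1 as follows.

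- Test household income and one named baseline caregiver distress measure in the same mixed model as hypotheses 1 and 2. A pre-defined composite would serve, since the preliminary work already allows "creation of derived variables that summarize performance on measures that are highly inter-correlated".
- Keep moderator, group by moderator, moderator by visit and group by moderator by visit whatever their p-values. Confine any backward elimination with bootstrap to exploratory covariates.
- For each outcome, report every group by moderator estimate with its 95% interval.
- Designate one contrast per moderator in advance, either averaged over the follow-up visits or at 6 months, as the sponsor chooses. State that error rates are per outcome; hypotheses 1 and 2 list eight outcomes.
- Derive the post hoc contrasts at moderator levels from this full model and label them descriptive.

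**Cost.** SAP wording only, since the mixed model is already planned. Non-significant interactions will be shown with wide intervals: at N = 200 the half-width is 1.96 × 0.085 to 1.96 × 0.100, about 0.17-0.20 SD per SD, for the averaged contrast, and about 0.20-0.24 at 6 months. A single-visit contrast or a split alpha loses some power. For b = 0.2 at both visits, the averaged contrast misses in 35-48% of trials (45-60% at 0.025) and the 6-month contrast in 49-63% (60-73% at 0.025). If the effect is present at 6 months only, the order reverses: 78-83% for the averaged contrast against 49-63% for the 6-month contrast, both at 0.05.

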6.1 Data Safety and Monitoring Plan

Risks to the patient and family's privacy are minimal, and every effort will be made to safeguard confidentiality according to HIPAA specifications. Personnel involved in data collection will be instructed regarding the importance of confidentiality and the steps that must be taken to protect it. Confidentiality of participant's names will be ensured by replacing names with subject numbers. The master list linking the two will be kept in a locked file drawer.

A licensed psychologist and staff trained in working with families of children and teens with TBI will be conducting this study. Participants and their families will be able to reach the study PI or designee to report any adverse effects or concerns.

Participants will complete a W9 form embedded in the REDCap survey to obtain compensation. After a participant completes the W9, this information will be uploaded to Cincinnati Children's Hospital Medical Center secured G: Drive and deleted from REDCap. All data will be presented and published in aggregate form without identifying information. All paper and pencil data will be secured in locked file cabinets and on-line data will be password protected and encrypted using 128-bit encryption software. Should participants disclose any unnecessary PHI on the questionnaires; the PHI will be redacted using black permanent marker and will be initialed and dated by the coordinator noting redacted PHI. PHI will also be edited out in audio recordings as well as resultant transcripts.

7. Quality Assurance and Quality Control

7.1 Quality Control Procedures

Regular meetings of the PI and project staff will serve to review recruitment, baseline, and follow-up assessment scheduling and completion, to address questions regarding administration and scoring of assessments, and to evaluate progress toward study milestones.

8. Human Subject Considerations

8.1 Potential Risks

Participants will encounter no more than minimal risks due to enrollment in this study. All of the questionnaire measures have been used extensively in previous research with no negative psychological reactions reported.

8.2 Potential Benefits

Regardless of the intervention condition the participant is assigned to, they will be provided links to resources on pediatric TBI that may be helpful.

9. Compensation and Costs

9.1 Compensation

Participants will be compensated as follows:

- \$50 after completing the first set of online questionnaires (baseline)

- \$50 after participating in the online self-guided intervention (or control condition) and completing the 1 to 1.5 month online questionnaires
- \$50 after completing the 6-month follow-up online questionnaires
- \$25 to parents who participate in the qualitative interview

